Transplantation of gut microbiota from a healthy human adult into germ-free mice resulted in all bacterial phyla, 92% of bacterial classes and 88% of genus-level taxa being detected in the feces of recipient germ-free mice^[37]. Human gut bacteria-containing mice fed a high-fat western diet gained significantly more adiposity during the two weeks following transplantation than mice that consumed a low-fat, plant polysaccharide-rich diet^[37], evidence that demonstrates a causative role for diet-induced increases in adiposity by human gut bacteria. Similarly, transplantation of human gut microbiota from 3 twins (2 female and 1 male) discordant for obesity into germ-free mice resulted in ~75% of family-level bacterial taxa and 99.7% of the functions encoded by the donor's microbiome being represented in recipient mice, thereby resulting in a greater increase in adiposity in mice colonized with fecal microbiota from obese, when compared with its lean co-twin^[38].

Collectively, these studies demonstrate that transfer of gut bacteria from humans into germ-free mice is highly efficient, functions encoded by the transferred microbiome are maintained, and phenotypes are transmissible. The objective of **AIM 2** is to test the causative role of human gut bacteria on the maintenance of lean mass and physical function by transferring fecal microbiota from HF and LF older adults into germ-free mice.

Statistical Power: Germ-free mice colonized with fecal bacteria from obese humans gained significantly more adiposity than germ-free mice colonized with fecal bacteria from their lean co-twin ($10.0\% \pm 5.0\%$ compared with $0.1\% \pm 2.0\%$), a result that was significant 15 days after colonization^[38]. Based on these data, the resulting effect size of 2.6 is sufficient to obtain 99% power at a type-I error probability of 0.05 with a sample size of 12 human subjects. Accordingly, with the goal of identifying a similar change in lean mass and physical function, I propose to transfer fecal bacteria from 12 older adults into germ-free mice.

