III.2.a Colonization of germ-free mice with human gut bacteria from HF and LF older adults: Fecal samples from 6 HF (3 males, 3 females) and 6 LF (3 males, 3 females) older adults will be transferred into sex-matched (with the goal of minimizing sex-associated gut microbial variability^[6, 7]) C57BL/6J germ-free mice for a duration of 5 weeks at the Germ-Free and Gnotobiotic Microbiology Core at the Harvard Digestive Disease Center (HDDC; Boston, MA). The transmissible effect of host phenotype by gut microbiota has been previously reported by transferring human fecal bacteria into C57BL/6J germ-free mice^[36-38]. Furthermore, the homogenous genetic background provided by inbred C57BL/6J germ-free mice allows for a cleaner system to dissect signals from gut bacteria-host interactions, and improves experimental reproducibility, when compared with genetically heterogeneous GFM^[39]. One fecal sample from each human donor will be transferred into 5 separate germ-free mice (based on the range of germ-free mice used in human fecal transfer experiments^[36, 38]), resulting in 60 mice colonized with human gut microbiota. 5 germ-free mice will not be colonized with fecal bacteria from older adults (germ-free control group). All recipient mice will be fed *ad libitum* with a commercial, sterilized mouse chow^[38]. Food consumption will be measured daily to ensure that changes in lean mass or physical function do not result because of differences in food intake.

III.2.b Measurement and analysis of the change in lean mass and physical function in mice colonized with human gut bacteria: Lean mass and physical function in mice colonized with human gut bacteria will be measured on day 0 (prior to colonization), 9, 18, 27 and 35 days post-colonization at the HDDC. Lean mass will be measured with use of quantitative magnetic resonance imaging (EchoMRI-3in1 instrument, Houston, TX)^[38]. Muscle strength will be measured using a grip strength meter for mice (Technical and Scientific Equipment GmbH, Bad Homburg, Germany)^[40]. Each mouse will firmly grab the pulling bar of the grip strength meter with both forepaws and then pulled gently backwards until it releases its grip. The peak force of each trial is considered the grip strength. A 1-liter beaker filled with water will be used as a swimming pool to test endurance capacity^[41].

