A weight (10% of body weight) will be attached to the tail of a mouse, which is then placed in the water. The amount of time that the mouse is able to maintain complete buoyancy will be recorded. The EchoMRI, grip strength meter and beaker/weight will be sterilized prior to use to ensure that germ-free conditions at the HDDC are maintained. Because [name] has previously measured lean mass and physical function in mice^[42, 43], he will perform these measurements at the HDDC.

Differences for the change in lean mass and physical function will be calculated relative to initial values. Statistical significance for the change in lean mass and physical function will be compared in mice colonized with fecal bacteria from HF or LF human donors and for germ-free mice that were not colonized with human gut bacteria with use of two-way ANOVA^[38].

III.2.c Bacterial taxa identification and association with the change in lean mass and physical function in mice colonized with human gut bacteria: Fecal pellets will be obtained from 5 germ-free mice at baseline, which will not be colonized with human gut bacteria. Five weeks post-colonization with human gut bacteria, fecal pellets will be collected from 60 mice (30 each from the HF and LF donors) and from the 5 germ-free mice that did not receive human gut bacteria. 16S rRNA gene profiling on these 70 fecal pellets will be performed as described in **Section III.1.a**.

Associations between gut bacteria-containing principal components and individual bacterial taxa with the 35-day change in lean mass, mouse grip strength and endurance capacity will be identified as described in **Section III.1.b**. Supervised machine learning (random forest) will be used to predict whether a sample came from a mouse colonized with HF or LF donor microbiota^[44].

The gut bacterial profile that is associated with the change in lean mass and physical function in mice colonized with HF or LF human fecal bacteria is expected to be similar to the gut bacterial profile that is associated with differentiation of HF from LF older adults. CIA will be used to identify associations between circulating metabolites with gut bacteria that collectively differentiate mice colonized with HF or LF gut bacteria.

A. Subject Characteristics

1) Subject eligibility criteria:

a) Inclusion criteria:

- i) Willing and able to sign the IRB approved informed consent form
- ii) Male and Female: males, 70-85y; females, 70-80y

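### The mouse outcomes are analysed as change from day 0 without the day-0 value as a covariate, which generally costs some precision and leaves the contrast sensitive to chance day-0 imbalance

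*Protocol*

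**What the plan says.** Section III.2.b is worded identically in the Protocol and the SAP. Lean mass, grip strength and swim endurance "will be measured on day 0 (prior to colonization), 9, 18, 27 and 35 days post-colonization". On the analysis, the section says: "Differences for the change in lean mass and physical function will be calculated relative to initial values". The comparison covers mice given HF-donor bacteria, mice given LF-donor bacteria and uncolonized mice; the text ends "for germ-free mice that were not colonized with human gut bacteria with use of two-way ANOVA".

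Neither document names the two ANOVA factors, says whether change is absolute or percent, or mentions a day-0 covariate. Section III.2.c carries the 35-day change forward into the association analyses.

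Section III.2.a gives the design: 6 HF and 6 LF donors (3 men and 3 women each), 5 sex-matched mice per donor, and 5 uncolonized controls. The Aim 2 power paragraph relies on "the resulting effect size of 2.6" and claims "99% power at a type-I error probability of 0.05 with a sample size of 12 human subjects".

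**The concern.** A change score fixes the slope of follow-up on day 0 at 1. If the true slope is lower, subtraction carries day-0 noise into the outcome and over-corrects any day-0 difference between groups. A covariate lets the data set the slope. Because day 0 is measured before colonization, donor bacteria cannot have affected it, so adjusting for it removes none of the effect under study.

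At stake is precision in an experiment with only 12 donors. The power claim also borrows its effect size from adiposity, which is not one of the outcomes to be analysed.

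**Working it through.** **Inputs from the documents.** 6 vs 6 donors, 5 mice per donor (30 vs 30 colonized mice), 5 controls (III.2.a). Means and SDs of 10.0 (5.0) and 0.1 (2.0) percent, effect size 2.6, alpha 0.05, power 99% (Aim 2 power paragraph).

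**Assumptions.** The documents give no correlation and no donor variance. I take rho, the within-donor correlation between day-0 and follow-up values, from 0.3 to 0.9, and the donor intraclass correlation (ICC) of follow-up values from 0 to 0.3. SDs at day 0 and follow-up are taken as equal unless stated.

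**1. The plan's own figure.** Pooled SD = sqrt((5² + 2²)/2) = 3.81, and 9.9/3.81 = 2.60. With 6 vs 6 and a two-sided t test (10 df), power is 98.1%; the normal approximation gives 99.5%. The stated 99% reproduces.

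**2. Ceiling on the gain.** With equal SD s and no donor variance:
- Var(change) = 2(1-rho)s²
- Var(adjusted) = (1-rho²)s²
- Ratio = (1+rho)/2, so the reduction is (1-rho)/2.

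**3. With donor variance.** Set the variance among mice within a donor to 1 and donor variance to t = ICC/(1-ICC). For means of 5 mice:

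ratio = [t + (1-rho²)/5] / [t + 2(1-rho)/5]

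| rho | ICC 0 | ICC 0.1 | ICC 0.3 |
|---|---|---|---|
| 0.3 | 0.65 | 0.75 | 0.86 |
| 0.5 | 0.75 | 0.84 | 0.92 |
| 0.7 | 0.85 | 0.92 | 0.97 |
| 0.9 | 0.95 | 0.99 | 1.00 |

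At ICC 0.3, t = 0.429 and the reduction at rho 0.3 is 14%. If donor variance is instead set at 0.3 of the mouse variance (t = 0.3), it is (0.3 + 0.182)/(0.3 + 0.28) = 0.83, or 17%. At rho 0.9 the reduction is 1% or less either way.

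**4. Level of the covariate.** The table treats the slope as known. Estimating it adds a factor of about 1 + 1/(v-2), where v is the degrees of freedom available for the slope.
- Within donors, v = 12 × 4 = 48 and the factor is 1.02 when ICC is 0. Simulated ratios were about 0.67 to 0.98 at ICC 0 and 0.86 to 1.00 at ICC 0.3.
- On 12 donor means with group and sex fitted, v = 9 and the factor is 1 + 1/7 = 1.14. At ICC 0 the ratios become 0.74, 0.86, 0.97 and 1.09; at ICC 0.3 they become 0.98, 1.05, 1.10 and 1.14. Several exceed 1.

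**5. Chance imbalance.** In units of the day-0 SD:
- 30 vs 30 mice: SE = sqrt(1/30 + 1/30) = 0.26
- 30 vs 5 controls: SE = sqrt(1/30 + 1/5) = 0.48

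Given an imbalance, the change contrast shifts by -(1-rho) times it. A one-SE imbalance at rho 0.7 gives 0.3 × 0.26 = 0.08 SD for HF vs LF and 0.3 × 0.48 = 0.14 SD against controls. At rho 0.3 the figures are 0.7 × 0.26 = 0.18 and 0.7 × 0.48 = 0.34. In simulation the average bias of the change contrast was zero to within 0.01 SD, and adjustment brought the dependence on imbalance to about zero.

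**6. Power, two-sided t, 6 vs 6.** The effect is held fixed on the change scale. The ICC 0 column gives up one degree of freedom for the covariate (9 df). The ICC 0.3 column keeps 10, because a within-donor slope costs none at donor level.

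| Effect | Change score | Adjusted, ICC 0 (rho 0.3, 0.5, 0.7, 0.9) | Adjusted, ICC 0.3 (same rho) |
|---|---|---|---|
| 2.6 | 98.1% | 99.9, 99.6, 99.1, 98.3% | not needed |
| 1.8 | 80.2% | 92.9, 89.2, 85.2, 81.2% | 85.6, 83.3, 81.5, 80.4% |
| 1.3 | 52.9% | 70.1, 64.0, 58.6, 54.0% | 59.1, 56.3, 54.3, 53.1% |

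The effects 1.8 and 1.3 are illustrations; 1.8 is about the smallest effect that 6 vs 6 detects with 80% power.

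**The case against.** The strongest reply is that change from baseline is a valid analysis and that, at the effect the plan assumes, power is already 98.1%. That stands. The larger gains need a smaller effect than the plan states. The reason not to stop there is that 2.6 was observed for adiposity, and the documents give nothing comparable for lean mass, grip or swim time.

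A second reply is that the equal-SD formula may not apply. The slope is rho times the ratio of follow-up SD to day-0 SD. If that ratio is 1.25 (an assumption), the slope at rho 0.8 is 1.25 × 0.8 = 1.0 and adjustment gains nothing; at rho 0.7 it gains about 2%. The formula also does not describe percent change, which the wording allows and the power inputs use. Both points stand. They make the size of the gain uncertain without giving a reason to fix the slope at 1.

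Three stronger readings are tempting and lack support:
- A reader might infer that six donors per group make a day-0 imbalance likely. Donors cannot influence a value taken before colonization; the imbalance depends on the 30 vs 30 or 30 vs 5 mice.
- A reader might infer that grip and swim time have slopes well below 1. That is plausible, but the documents report no reliability or correlation for any mouse measure.
- A reader might infer that adjustment is at least as precise at every correlation. Step 4 shows this fails if donor means are analysed.

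**Conclusion.** The point holds as a worthwhile improvement. The documents do not support calling the planned analysis biased or invalid: under random allocation the change contrast is unbiased on average. Neither document describes how mice are allocated to donors beyond sex matching, so random allocation is itself an assumption.

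With equal SDs, the variance reduction is at most 35%, 25%, 15% and 5% at rho 0.3, 0.5, 0.7 and 0.9. With donor ICC 0.3 it falls to about 14 to 17% at rho 0.3, depending on how donor variance is scaled, and to 1% or less at rho 0.9. The power gain is under 2 points at an effect of 2.6. At an effect of 1.8 it runs from about 0.2 to 13 points across the assumed range. The comparison with the five controls is the more exposed to chance imbalance. Rho, ICC and the SD ratio are all assumed.

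**What to change.** In section III.2.b of both Protocol and SAP, replace the ANOVA of changes with a model of the follow-up value (day 35, or days 9 to 35 jointly):
- each mouse's own day-0 value as a mouse-level covariate;
- group, sex and, for the joint analysis, day as fixed factors;
- donor as a random effect, and mouse as well when several days are modelled together.

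State that the adjustment is not to be run on the 12 donor means. Report change scores descriptively and say whether they are absolute or percent. State how the five controls, which have no donor, enter the model.

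The data are already due to be collected. The cost is a short SAP edit, one degree of freedom and a slightly more complex model.

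### Aim 2 mouse comparison (III.2.b): four changes per mouse share one day-0 value, but the named two-way ANOVA has no stated factors and no mouse or donor term; if day is a factor and mouse is not, HF v LF false positives are about 22% at an assumed correlation of 0.5

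*Protocol*

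**What the plan says.** Section III.2.b is worded alike in the protocol and the SAP. Lean mass and physical function in colonized mice "will be measured on day 0 (prior to colonization), 9, 18, 27 and 35 days post-colonization at the HDDC". The next step is that "Differences for the change in lean mass and physical function will be calculated relative to initial values", so all four changes of a mouse are taken from one reading. HF-colonized and LF-colonized mice are then compared with each other and with "germ-free mice that were not colonized with human gut bacteria with use of two-way ANOVA", with a citation to the obesity-discordant twin transfer study.

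The design is in III.2.a: "One fecal sample from each human donor will be transferred into 5 separate germ-free mice", from 6 HF and 6 LF donors, giving 30 mice per condition; and "5 germ-free mice will not be colonized with fecal bacteria from older adults (germ-free control group").

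Neither document names the two ANOVA factors, says which day or days are tested, or mentions a repeated-measures, mouse or donor term. No variance or correlation of the mouse readings is given. The sentence that sets the measurement days refers to colonized mice only, so the controls' schedule is not stated.

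**The concern.** Condition and measurement day are the two structured dimensions that III.2.b itself describes, so condition by day is the natural reading. Where the plan wants one time point it says so: III.2.c uses the 35-day change, whereas III.2.b sets no such limit.

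Four changes from one mouse are not four independent observations. They contain the same day-0 reading, and mice may also differ persistently in growth. A condition-by-day ANOVA without a mouse term ignores this. Its error term is too small for the condition main effect and too large for the condition-by-day interaction. The first could make noise look like an HF v LF difference; the second could hide a modest divergence after colonization. This comparison carries Aim 2's test of a causative role.

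The issue is separate from mice sharing a donor: it is present when donors contribute nothing.

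**Working it through.** **1. The plan's own figure.** The Aim 2 power statement says that "the resulting effect size of 2.6 is sufficient to obtain 99% power at a type-I error probability of 0.05", with 12 donors. From the quoted means and SDs, d = (10.0 − 0.1)/√((5.0² + 2.0²)/2) = 9.9/3.808 = 2.60. With 6 v 6, power is 99.5% (normal approximation), 98.1% (two-sided t, 10 df) or 99.4% (one-sided t). The figure reproduces, and it counts donors as the sample. The documents give no false-positive rate for the ANOVA beyond the nominal 0.05.

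**2. Correlation from the shared baseline.** Assume equal residual variance s² at each visit and errors independent given the mouse. Then Var(Yₜ − Y₀) = 2s² and Cov(Yₜ − Y₀, Yᵤ − Y₀) = s², so ρ = 0.5. This ρ is an assumption, not a figure from the plan.

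**3. HF v LF main effect, condition by day, no mouse term, no donor effect.** With four changes per mouse, the variance of the HF − LF difference is understated by about 1 + 3ρ. False-positive rate = 2[1 − Φ(1.96/√(1 + 3ρ))]:

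| ρ (assumed) | 1 + 3ρ | 1.96/√(1 + 3ρ) | false positives |
|---|---|---|---|
| 0 | 1.0 | 1.960 | 5.0% |
| 0.2 | 1.6 | 1.549 | 12.1% |
| 0.3 | 1.9 | 1.422 | 15.5% |
| 0.5 | 2.5 | 1.240 | 21.5% |
| 0.7 | 3.1 | 1.113 | 26.6% |
| 0.9 | 3.7 | 1.019 | 30.8% |

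Simulation of 30 v 30 mice at ρ = 0.5 (20,000 runs) gave 21.3%. It gave 5.1% with mouse as the error unit and 4.9% with the day-35 change alone.

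Other covariance structures, also simulated:
- serially correlated readings (9-day correlation 0.3 to 0.9): 23% to 25%
- mouse-specific slopes: 23% to 24%
- random walk: 26%
- day-0 residual variance half, or a quarter, of later days: 16%, or 12%

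**4. Condition-by-day test (HF v LF, 3 df).** Without a mouse term it rejects about 0.2% of the time under no divergence at ρ = 0.5. For power, assume that HF and LF diverge linearly from 0 at day 9 to 0.8 SD at day 35. The differences are 0.8(day − 9)/26 = 0, 0.277, 0.554 and 0.8. Their sum of squares about the mean is 0.3586, and × 15 gives 5.379, so the noncentrality is 5.379/(1 − ρ).

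| ρ | noncentrality | power, no mouse term | power, repeated-measures test |
|---|---|---|---|
| 0.3 | 7.68 | 40% | 62% |
| 0.5 | 10.76 | 34% | 78% |
| 0.7 | 17.93 | 26% | 95% |

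Repeat simulations lay within about 3 points of these values.

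**5. Is one value per mouse enough?** Only if donors contribute nothing. Five mice share each donor. Let the donor intraclass correlation (ICC) of a single change be 0.1 or 0.2 (assumed), with ρ = 0.5.
- Mean of the four changes: its variance is (1 + 3 × 0.5)/4 = 0.625, so the donor share is 0.1/0.625 = 0.16 or 0.2/0.625 = 0.32. The design effect 1 + 4 × share is 1.64 or 2.28, and false positives are about 13% or 19%.
- Day-35 change: the design effect is 1 + 4 × ICC = 1.4 or 1.8, and false positives are about 10% or 14%.
- One value per donor (t test, 10 df): about 5% in each case by simulation.

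**The case against.** The strongest objection is that this is an unspecified model, not a demonstrated error. A two-way ANOVA can be a repeated-measures one, and the documents do not show how the cited study applied it. Sex is a possible second factor: donors are balanced by sex and mice are sex-matched. Condition by sex on the 35-day change would be coherent, and the problem would not arise. The power basis is also a single-time-point difference. This stands, so every figure here is conditional.

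Three stronger readings are tempting, and the documents do not support them.
- **That the plan commits to an ordinary ANOVA with day as a factor.** It names neither. Against the sex reading, sex-matching is given only as a way to limit microbial variability and is never named as an analysis factor. That makes condition by day likelier, but not certain.
- **That 21% to 22% is the error rate, or a floor set by the shared baseline.** It rests on ρ = 0.5. A less noisy day-0 reading lowers it; serial correlation or mouse-specific growth raises it.
- **That the interaction test always loses more than half its power.** At ρ = 0.3 the loss is about a third, and the 0.8 SD divergence is assumed. With 30/30/5 mice and the same four days assumed for the controls, both tests exceed 96% power at 1.6 SD and reach 100% at 2.6 SD, the size of effect on which the plan bases its power.

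Rates that involve the germ-free mice need that same unstated schedule, so the main figures above are for HF v LF only.

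**Conclusion.** The point holds in conditional form. III.2.b leaves the two factors, the day or days tested, and the mouse and donor terms undefined. On its likeliest reading, fitted without a mouse term, the HF v LF main effect rejects about 22% of the time at ρ = 0.5, and about 12% to 31% for ρ from 0.2 to 0.9, against a nominal 5%. This assumes no donor effect; a donor effect would add to it. The condition-by-day test is conservative and loses power for modest divergences, but not for effects as large as the plan targets. If only one day's change is tested, the within-mouse problem disappears and only donor clustering remains. The model should be fixed before the mouse data are seen, because one admissible reading holds its error rate (apart from donor clustering) and the likelier one does not.

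**What to change.** In III.2.b of both documents, replace the two-way ANOVA with one of the following.

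- **All four days.** A linear mixed model with condition (HF, LF, germ-free), day (9, 18, 27, 35) and condition × day as fixed effects, and random effects for donor and for mouse within donor (mouse only for the germ-free controls). Use small-sample degrees of freedom, so that HF v LF is tested against between-donor variation.
- **One day.** Name the 35-day change, already used in III.2.c, as the single tested outcome, analysed with a donor random effect or as 12 donor means.

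A within-mouse covariance alone, or one value per mouse with no donor term, is not enough, because it leaves the five mice per donor uncorrected. If the germ-free mice enter the model, state their measurement days.

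The cost is a few sentences and a standard model, with no new animals or data. Main-effect intervals widen by about √2.5 = 1.58 at ρ = 0.5 before any donor variance, which is their correct width. Testing against donors matches the plan's own power statement, which already counts 12 donors.

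### The mouse test of causality states no deciding contrast, day or outcome, and nothing controls error across its three outcomes

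*Protocol*

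**What the plan says.** The Protocol states Aim 2, and the SAP repeats it in the same words, as a test of a causative role for human gut bacteria. Its statistical power paragraph uses an adiposity result from a cited twin study and concludes that "the resulting effect size of 2.6 is sufficient to obtain 99% power", with one type-I error of 0.05 and 12 donors. Sidedness is not given.

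Section III.2.a sets the groups. The donors are described as "Fecal samples from 6 HF (3 males, 3 females) and 6 LF (3 males, 3 females) older adults", each donor supplies 5 mice, and 5 further mice stay germ-free. Section III.2.b gives three outcomes (lean mass, grip strength and a weighted swim test), which "will be measured on day 0 (prior to colonization), 9, 18, 27 and 35 days post-colonization". The analysis sentence follows: "Statistical significance for the change in lean mass and physical function will be compared in mice colonized with fecal bacteria" from HF or LF donors, and in the germ-free mice, by two-way ANOVA on change from initial values.

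Section III.2.c refers to "the 35-day change in lean mass, mouse grip strength and endurance capacity", but only for associations with bacterial taxa. Neither document names the ANOVA factors, the contrast or day that decides Aim 2, a primary mouse outcome, or a multiplicity adjustment.

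**The concern.** The power statement describes one comparison at 0.05. The analysis offers three outcomes and three groups, and no rule says which result would establish the causal role. If any one significant outcome can be reported as showing it, the 0.05 in the power paragraph is not the error rate of the conclusion.

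The choice of contrast matters as well. The scientific question is HF versus LF donors. An overall test of three groups can reject because uncolonized mice differ from all colonized mice, even if HF and LF recipients are alike. That result would say something about colonization and nothing about donor function.

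**Working it through.** **Inputs.** From the power paragraph for Aim 2: means 10.0 and 0.1, SDs 5.0 and 2.0, type-I error 0.05, 12 donors. From III.2.a: 6 HF and 6 LF donors. From III.2.b: three outcomes and four post-colonization days. Assumed, because the documents are silent: correlations between outcomes from 0 to 0.9, correlations between days from 0.5 to 0.9, two-sided tests, and the donor as the unit of analysis.

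**The plan's own figure.**
- SD = sqrt((5.0² + 2.0²)/2) = sqrt(14.5) = 3.808.
- d = (10.0 − 0.1)/3.808 = 9.9/3.808 = 2.60.
- Noncentrality with 6 versus 6 = 2.60 × sqrt(6/2) = 4.50.
- Two-sided power at 0.05: 99.5% by the normal approximation, 98.1% by noncentral t on 10 df. One-sided noncentral t gives 99.4%.

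The stated 99% reproduces for a single test.

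**Error over three outcomes, one HF-versus-LF test each at 0.05.**
- Independent outcomes: 1 − 0.95³ = 14.3%.
- Correlated outcomes, by simulation of donor-level t tests under the global null (100,000 runs):

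| Between-outcome correlation | Chance of at least one false positive |
|---|---|
| 0 | 14.3% |
| 0.3 | 13.8% |
| 0.5 | 12.9% |
| 0.8 | 10.1% |
| 0.9 | 8.7% |

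**If each day were also tested separately (3 × 4 = 12 tests).**
- Independent tests: 1 − 0.95¹² = 46.0%, which is a ceiling only.
- Same simulation over the assumed correlations: 16.3% (outcomes 0.9, days 0.9) to 40.7% (outcomes 0, days 0.5). With outcomes at 0.5 and days at 0.8 it is 28.9%.

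**Price of control.** Holm over three outcomes holds family-wise error at or below 5%. Its strictest step uses 0.05/3 = 0.0167. At that level and d = 2.6, power is 98.3% (normal) or 92.4% (noncentral t). Later Holm steps use larger levels, so 92.4% is the floor for each outcome that truly has this effect.

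**The case against.** The best defence is that III.2.b lists days on which measurements are taken, not 12 tests. If the two ANOVA factors are group and time, each outcome has one model and the days do not multiply. This stands. A reader might infer a 46% error rate, but the documents do not support it: daily testing is not stated, and the days are repeated measures on the same mice, all expressed against the same day-0 value, so independence is unrealistic. The three-outcome figure of 9% to 14% survives the defence.

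A second objection is that inflation depends on treating any single positive outcome as proof. This also stands as a condition. The plan neither states nor excludes such a rule. If all three outcomes had to be significant, error would not be inflated, and a claim confined to one outcome fixed in advance would carry only its own 5%. But no rule of either kind is written.

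A third is that III.2.c already makes day 35 the endpoint. It does so for the taxa associations only, although this makes day 35 the natural choice for the group comparison.

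Finally, this is a pilot. That word does describe the study in the safety monitoring section, but Aim 2 has its own power statement and is worded as a causal test. Neither document calls the mouse experiment exploratory.

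**Conclusion.** The gap is real and should be closed. As written, Aim 2 has no stated success rule. Under an any-one-outcome rule the error of the causal claim is about 9% to 14%, not 5%, with one HF-versus-LF test per outcome. Separate testing of days would raise it by an amount that depends on correlations the documents do not give. The risk that an overall three-group test rejects because of the germ-free mice is additional and is not quantified here.

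A reader might infer that the power calculation is wrong. It is not: 99% reproduces for a single comparison. What is missing is the link between that comparison and the conclusion. All figures here take the donor as the unit; how the 5 mice per donor enter the ANOVA is a separate matter.

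**What to change.** State the ANOVA factors in III.2.b of both documents. Add that the causal conclusion rests on the HF-versus-LF contrast in the 35-day change, tested with Holm across lean mass, grip strength and swim endurance at an overall two-sided 0.05. Report earlier days and germ-free contrasts as supportive.

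An equally sound alternative is to name one primary outcome at 0.05 and test the other two, with Holm, only if it succeeds. The documents do not rank the outcomes, so the choice is the sponsor's. The gate is essential. One outcome at 0.05 with ungated Holm on the other two would leave 1 − 0.95 × 0.975² = 9.7% if the outcomes are independent.

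The text change is a few sentences. Under Holm each outcome needs somewhat stronger evidence: power at d = 2.6 with 6 versus 6 donors falls from 98.1% to no lower than 92.4% (noncentral t). This borrows the plan's assumption that an adiposity effect size carries over to lean mass and function. With a gated primary, that outcome keeps 98.1%. Either way, germ-free contrasts no longer carry a confirmatory claim.
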